#### **MTD and Expansion Cohort Analysis**

The efficacy endpoint is progression-free survival (PFS) and overall survival (OS) of the patients enrolled in the expansion cohort and those treated at the MTD dose.

The duration of PFS is defined as the time from the beginning of the first cycle of treatment to the date of progressive disease or death from any cause whichever occurs first.

The duration of OS is defined as the time from the beginning of the first cycle of treatment to the date of death from any cause.

Both time-to-event variables, PFS and OS, will be estimated by the Kaplan-Meier method, estimates of survival in reported at 6, 12, 18, 24, 30 and 36 months and the corresponding 95% confidence intervals will be reported.

Toxicity rate in the expansion cohort will be evaluated and summarized using frequency and a corresponding exact binomial 95% confidence interval.

All subjects treated with an investigational product will be included in the analysis.

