#### **Stopping Guidelines**

Based on prior studies such as the Ibrutinib–rituximab combination study by Wang et al (2016), an estimated rate of toxicity around 10-12% would be considered acceptable in lymphoma patients. Because it is a new combination adding venetoclax to ibrutinib +rituximab, there is a built-in dose escalation in the phase I part of the study. Regarding the expansion phase there is not yet clear data available to predict the toxicity profile over time. The addition of venetoclax to ibrutinib has been tested in mantle cell lymphoma in a rather small series with impressive activity (different lymphoma subtype though) with 17/24 pts experiencing grade 3 or more AE, mostly GI (diarrhea) and increased myelotoxicity (neutropenia but no increased infection / thrombocytopenia) 2 AFIB and 2 tumor lysis syndrome. All were managed with supportive care and again this was in a different disease setting.

Given the lack of prior reference we believe that a 10% toxicity would be expected and that a 30% rate of cumulative related toxicity would be considered unacceptable in this population. The DSMC will also be monitoring the trial to review potential toxicities as per standard procedure.

Employing monitoring based on repeated significance testing and using O'Brien-Fleming boundary type boundary, for a maximum of 24 patients in the expansion cohort, 10.0% as lower proportion and 10% alpha level, i.e. probability of crossing the boundary under assuming acceptable toxicity is 10.0%, an 80% power for the detection of crossing the boundary of high toxicity by at least 30%, a shape parameter,  $\delta=0.1$ , the following stopping guidelines were computed using the *Clinfun* package version 1.0.15(2018) in R software(R Foundation for Statistical Computing, Vienna, Austria).

Table 1. Stopping Boundaries for Venetoclax +(Ibrutinib/Rituximab) Toxicity

Monitoring Look	Number of Patients at Monitoring Look	Stop if Number of Toxicities is at least
1	5	3
2	11	4
3	17	5
4	24	6

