Table 1 shows boundary is for the experimental drug combination, Venetoclax +ibrutinib/rituximab), to monitor patients who experience high toxicity. If out of the first 5 patients, 3 or more experience high toxicity then the trial will be stopped. If at least 4 out of the first 11 patients experience high toxicity, then the trial will be terminated. If at least 5 out of the first 17 patients have high toxicity due to Venetoclax + (ibrutinib/rituximab), then the trial will be stopped. If at least 6 out of the 24 patients report high toxicity due to venetoclax + (ibrutinib/rituximab), then the combination will be deemed too toxic for patients with relapsed/refractory diffuse large B-cell non-Hodgkin's lymphoma.

Table 2. Operating Characteristics of the Stopping Rule for Safety (n=24)

	Toxicity Rate	Probability of crossing low boundary	Probability of stopping low boundary	Expected sample size low boundary	Probability of crossing high boundary	Probability of stopping high boundary	Expected sample size high boundary
1	0.100	0.053	0.049	23.4	0.047	0.043	23.5
2	0.118	0.092	0.086	23.0	0.084	0.077	23.2
3	0.136	0.146	0.135	22.5	0.135	0.123	22.7
4	0.155	0.211	0.196	21.8	0.198	0.182	22.1
5	0.173	0.286	0.267	21.0	0.272	0.250	21.4
6	0.191	0.368	0.344	20.2	0.353	0.327	20.5
7	0.209	0.453	0.425	19.2	0.438	0.407	19.6
8	0.227	0.536	0.506	18.2	0.522	0.489	18.6
9	0.245	0.615	0.584	17.2	0.602	0.568	17.6
10	0.264	0.688	0.657	16.1	0.677	0.643	16.6
11	0.282	0.752	0.723	15.1	0.743	0.710	15.6
12	0.300	0.808	0.781	14.1	0.800	0.770	14.6

From the last the last row of the operating characteristics of the stopping rule, it is seen that when the probability of toxicity  $>0.30$ , the trial will be halted with power of 0.81 based on the low boundary with expected sample size at the termination of 14.1 patients. Based on the high boundary, the trial in the expansion cohort will be terminated when the probability of toxicity more than 0.30 with a power of 0.77 at expected sample size of 14.6. If the trial toxicity is at least 0.30, the probability that the trial will cross the boundaries is at least 80%. These operating characteristics seem reasonable to stop the trial early for safety for a moderate sample of 24 patients.

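### The expansion toxicity rate is to be reported with a fixed-sample estimate and interval that ignore early stopping: a modest upward bias, and a lower limit that misses too often near the 10% acceptable rate

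*Combined protocol and SAP*

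**What the plan says.** Section 12, MTD and Expansion Cohort Analysis, gives the whole analysis of expansion toxicity in one sentence: "Toxicity rate in the expansion cohort will be evaluated and summarized using frequency and a corresponding exact binomial 95% confidence interval".

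The Stopping Guidelines in the same section put this cohort under sequential monitoring: "Employing monitoring based on repeated significance testing and using O'Brien-Fleming boundary type boundary", "for a maximum of 24 patients in the expansion cohort". The design values are "10.0% as lower proportion and 10% alpha level" and "an 80% power for the detection of crossing the boundary of high toxicity by at least 30" percent. The higher value is explained as follows: a "30% rate of cumulative related toxicity would be considered unacceptable in this population".

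Table 1 of the Stopping Guidelines sets limits of 3 at 5 patients, 4 at 11, 5 at 17 and 6 at 24. The text makes them binding, for example "If out of the first 5 patients, 3 or more experience high toxicity then the trial will be stopped" and "If at least 5 out of the first 17 patients have high toxicity". The look at 24 is full enrolment. It can label the combination too toxic but cannot shorten the cohort, so only three looks can stop it early.

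Section 12 adjusts neither the estimate nor the interval for these looks. The reference list in Section 15 does include a group-sequential textbook.

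**The concern.** The observed proportion is unbiased, and a Clopper–Pearson interval exact, when the number of patients is fixed in advance. Here the number depends on the toxicities seen. A cohort that closes at 5/17 closes because its count has just run high, and it never enrols the later patients who might have pulled the proportion back. The raw rate is then too high on average, and the lower limit can be too high as well.

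At stake is how the final safety estimate is read against the plan's own reference value. A stop at 5/17 gives a fixed-sample interval of 10.3% to 56.0%, which excludes the acceptable rate of 10%. An exact interval that allows for the looks gives 9.1% to 53.8%, which includes it.

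**Working it through.** **Inputs.** The limits 3/5, 4/11, 5/17 and 6/24 and the maximum of 24 come from Table 1 of the Stopping Guidelines. The rates 10% and 30% come from its text; 20% is added as a midpoint. The interval is the fixed-sample exact 95% interval of the analysis sentence, taken as equal-tailed (2.5% per tail). The reported toxicity is assumed to be the monitored high toxicity.

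**Method.** For an outcome of x toxicities in n patients, P(n, x) = W(n, x) · p^x · (1−p)^(n−x), where W counts the patient sequences that reach (n, x) without an earlier stop. Two readings were run: stopping only at the looks, as the text describes, and stopping as soon as the next look's limit is reached.

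**Reproducing Table 2 (high-boundary columns).**

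| True rate | Source | P(cross) | P(stop early) | Expected n |
|---|---|---|---|---|
| 10% | Table 2 | 0.047 | 0.043 | 23.5 |
| | Looks only | 0.0467 | 0.0343 | 23.57 |
| | Immediate | 0.0467 | 0.0429 | 23.52 |
| 30% | Table 2 | 0.800 | 0.770 | 14.6 |
| | Looks only | 0.7996 | 0.6437 | 15.84 |
| | Immediate | 0.7996 | 0.7700 | 14.61 |

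Both readings match the crossing probability. Only immediate stopping matches the other two columns. The low-boundary columns cannot be checked because only one set of limits is printed.

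**Path counts (looks only).**
- 3/5: W = C(5,3) = 10.
- 4/11: W = C(6,4) + 5·C(6,3) + 10·C(6,2) = 15 + 100 + 150 = 265.
- Open at 11 with 0, 1, 2 or 3 toxicities: 1, 11, 55 and 155 sequences.
- 5/17: W = 1·6 + 11·15 + 55·20 + 155·15 = 3,596.

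At p = 0.10 these three outcomes have probabilities 10 × 0.1³ × 0.9² = 0.0081, 265 × 0.1⁴ × 0.9⁷ = 0.0127 and 3,596 × 0.1⁵ × 0.9¹² = 0.0102. Counts above the limits bring the total for an early stop to 0.0343.

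**Lower-limit error at 10%.** Every early stop has a fixed-sample lower limit above 10% (14.7% at 3/5, 10.9% at 4/11, 10.3% at 5/17). At 24 patients, 6/24 does not (9.8%), but 7 or more does, with probability 0.0016 + 0.0002 = 0.0018. The miss rate is 0.0343 + 0.0018 = 0.0361, or 3.6%. With a fixed 24 patients it would be 0.75%. Under immediate stopping it is 4.3%.

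**Bias.** The mean of x/n is Σ (x/n)·P(n, x). As a check at 30%, looks only: early stops average 44.1% with probability 0.644, and completed cohorts average 21.9% with probability 0.356. So 0.644 × 0.441 + 0.356 × 0.219 = 0.284 + 0.078 = 0.362, a bias of +6.2 points.

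| True rate | Bias, looks / immediate (points) | Lower-limit miss, looks / immediate | Two-sided coverage, looks / immediate |
|---|---|---|---|
| 10% | +0.6 / +0.8 | 3.6% / 4.3% | 96.4% / 95.7% |
| 20% | +3.5 / +4.6 | 1.1% / 0.8% | 98.4% / 98.7% |
| 30% | +6.2 / +8.3 | 0.6% / 0.0% | 98.2% / 98.8% |

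Looks only, the lower-limit miss exceeds 2.5% for true rates of about 6.9–7.2%, 8.5–11.0%, 12.0–14.7% and 27.6–28.4%, with a maximum of 4.3% near 9.75%. Coverage is below 95% only at about 14.2–14.7%, with a minimum of 94.2%. The minimum under immediate stopping is 94.4%, near 14.3%.

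**Adjusted results for 5/17, looks only.** Under stage-wise ordering, the outcomes at least as toxic as 5/17 are all the early stops. At 10% their probability is 0.0343, above 0.025, so 10% stays inside the interval; solving for each limit gives 9.1% to 53.8%. The uniformly minimum-variance unbiased estimate (UMVUE) is the share of paths in which the first patient has a toxicity: 800/3,596 = 22.2%, against a raw 29.4%. At 10%, the stage-wise interval's lower-limit miss is 2.4%.

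**The case against.** The plan states one level, 95% two-sided, and by that standard the interval performs well. Its conservatism absorbs most of the effect of the looks, and coverage is above 95% at all three reference rates. This stands. A reader might infer that the reported interval generally fails its stated level, or that its lower limit is generally too high. The plan's own rule does not bear that out: the lower-tail excess is confined to narrow ranges, although one of them contains 10%.

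A reader might also take the mean reported rate after an early stop, 41% when the truth is 10%, as the typical distortion. That event has probability 3.4%. The unconditional bias there is 0.6 points.

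No decision uses the interval. Stopping and the too-toxic label rest on counts, and the documents do not say that later planning will use this estimate. At 5/17 the lower limit moves by 1.2 points and the cohort has closed either way. With 2/24 or fewer, nothing changes. The raw bias is also in the cautious direction. All of this limits the size of the point.

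The strongest objection is to the remedy. The unbiased estimate shrinks high counts hard: 11/24, raw 46%, becomes 20.3%, below the raw lower limit of 25.6%. In a safety report it cannot stand in for the observed rate. None of this answers the core point, that the planned estimate and interval take no account of the rule and the plan does not say so.

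**Conclusion.** The point holds as a modest bias and lower-tail problem. The raw rate overstates the true rate by 0.6 to 0.8 points at 10%, 3.5 to 4.6 at 20% and 6.2 to 8.3 at 30%, depending on the stopping reading. At 10% the lower limit is above the truth in 3.6% to 4.3% of trials, against 2.5% per tail. It is not a general failure of coverage, and it does not threaten the stopping decisions.

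Three assumptions carry these figures. The first is that the toxicity rate in the analysis sentence is the high toxicity being monitored. The documents do not say so, and a different event would change every number. The second is that the interval is equal-tailed. The third is the stopping reading: the text and Table 1 describe stops at looks, while the early-stopping and expected-size columns of Table 2 match immediate stopping. The range above covers both.

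**What to change.** Replace the analysis sentence in Section 12 with wording such as:

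> *The expansion toxicity rate is the proportion of patients with the high-toxicity event monitored under the Stopping Guidelines. The primary summary is the observed frequency with its exact binomial 95% interval, which do not account for the stopping rule. An estimate adjusted for the rule and an exact 95% interval based on stage-wise ordering will be shown beside them.*

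State in the Stopping Guidelines whether the cohort stops only at the looks or as soon as a limit is reached, and compute the adjusted results for that reading. For stops only at the looks:

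| Outcome | Raw rate (95% interval) | UMVUE (stage-wise 95% interval) |
|---|---|---|
| 3/5 | 60.0% (14.7–94.7%) | 60.0% (14.7–94.7%) |
| 4/11 | 36.4% (10.9–69.2%) | 30.2% (10.3–68.2%) |
| 5/17 | 29.4% (10.3–56.0%) | 22.2% (9.1–53.8%) |
| 6/24 | 25.0% (9.8–46.7%) | 18.6% (8.4–44.6%) |
| 3/24 | 12.5% (2.7–32.4%) | 12.3% (2.7–32.3%) |

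This table does not carry over to immediate stopping. There 3/5 means the third toxicity fell on patient 5, which gives C(3,1)/C(4,2) = 3/6 = 50%; 4/11 gives 27.3%; and stops between looks need their own rows.

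The cost is a few sentences and a short table, with no extra patients or data. The downside to disclose is the shrinkage when the count overshoots the limit (11/24 gives 20.3%), which is why the adjusted figure goes beside the raw rate and must not replace it.

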#### **DLT Definitions:**

The assessment of DLT will follow the guidelines provided in the Common Terminology Criteria for Adverse Events (CTCAE) version 4.0. A DLT is defined as:

##### Hematologic:

- Grade 3 neutropenia (ANC <1,000/mm^3) that does not resolve to  $\leq$  Grade 2 within 3 weeks with the use of growth factor
- Grade 4 neutropenia (ANC <500/mm^3)
- Febrile neutropenia (ANC <1,000/mm^3 with a fever  $\geq$ 38.3°C)
- Grade 4 thrombocytopenia (<25,000/ mm^3) that persists for  $\geq$ 7 days, despite holding treatment
- Grade 3 thrombocytopenia associated with Grade  $\geq$ 2 bleeding or requiring RBC or platelet Transfusions

##### Non-Hematologic:

- Any Grade 3 or higher non-hematologic adverse event where relationship to study drug(s) cannot be ruled out (Note: excludes rituximab infusion reactions)
- Grade  $\geq$ 3 nausea, vomiting, or diarrhea uncontrolled by maximal supportive care and persisting greater than 7 days
- Grade 3 fatigue persisting for greater than 7 days
- Treatment delay of any drug greater than 7 days for toxicity

In the Dose Escalation Phase, if a subject is non-compliant with the prescribed therapy or ends treatment within the first cycle for reasons other than study drug(s) related toxicity, ie, withdraws consent, they will be replaced. Any subject that misses  $>4$  doses of ibrutinib or venetoclax for reasons other than toxicity or subject that requires rituximab discontinuation during the first cycle will be replaced. Replaced subjects will be included in the ITT analysis.

There will be no intrapatient dose escalation.

#### **Stopping Guidelines**

Based on prior studies such as the Ibrutinib–rituximab combination study by Wang et al (2016), an estimated rate of toxicity around 10-12% would be considered acceptable in lymphoma patients. Because it is a new combination adding venetoclax to ibrutinib +rituximab, there is a built-in dose escalation in the phase I part of the study. Regarding the expansion phase there is not yet clear data available to predict the toxicity profile over time. The addition of venetoclax to ibrutinib has been tested in mantle cell lymphoma in a rather small series with impressive activity (different lymphoma subtype though) with 17/24 pts experiencing grade 3 or more AE, mostly GI (diarrhea) and increased myelotoxicity (neutropenia but no increased infection / thrombocytopenia) 2 AFIB and 2 tumor lysis syndrome. All were managed with supportive care and again this was in a different disease setting.

Given the lack of prior reference we believe that a 10% toxicity would be expected and that a 30% rate of cumulative related toxicity would be considered unacceptable in this population. The DSMC will also be monitoring the trial to review potential toxicities as per standard procedure.

Employing monitoring based on repeated significance testing and using O'Brien-Fleming boundary type boundary, for a maximum of 24 patients in the expansion cohort, 10.0% as lower proportion and 10% alpha level, i.e. probability of crossing the boundary under assuming acceptable toxicity is 10.0%, an 80% power for the detection of crossing the boundary of high toxicity by at least 30%, a shape parameter,  $\delta=0.1$ , the following stopping guidelines were computed using the *Clinfun* package version 1.0.15(2018) in R software(R Foundation for Statistical Computing, Vienna, Austria).

Table 1. Stopping Boundaries for Venetoclax +(Ibrutinib/Rituximab) Toxicity

Monitoring Look	Number of Patients at Monitoring Look	Stop if Number of Toxicities is at least
1	5	3
2	11	4
3	17	5
4	24	6

Table 1 shows boundary is for the experimental drug combination, Venetoclax +ibrutinib/rituximab), to monitor patients who experience high toxicity. If out of the first 5 patients, 3 or more experience high toxicity then the trial will be stopped. If at least 4 out of the first 11 patients experience high toxicity, then the trial will be terminated. If at least 5 out of the first 17 patients have high toxicity due to Venetoclax + (ibrutinib/rituximab), then the trial will be stopped. If at least 6 out of the 24 patients report high toxicity due to venetoclax + (ibrutinib/rituximab), then the combination will be deemed too toxic for patients with relapsed/refractory diffuse large B-cell non-Hodgkin's lymphoma.

Table 2. Operating Characteristics of the Stopping Rule for Safety (n=24)

	Toxicity Rate	Probability of crossing low boundary	Probability of stopping low boundary	Expected sample size low boundary	Probability of crossing high boundary	Probability of stopping high boundary	Expected sample size high boundary
1	0.100	0.053	0.049	23.4	0.047	0.043	23.5
2	0.118	0.092	0.086	23.0	0.084	0.077	23.2
3	0.136	0.146	0.135	22.5	0.135	0.123	22.7
4	0.155	0.211	0.196	21.8	0.198	0.182	22.1
5	0.173	0.286	0.267	21.0	0.272	0.250	21.4
6	0.191	0.368	0.344	20.2	0.353	0.327	20.5
7	0.209	0.453	0.425	19.2	0.438	0.407	19.6
8	0.227	0.536	0.506	18.2	0.522	0.489	18.6
9	0.245	0.615	0.584	17.2	0.602	0.568	17.6
10	0.264	0.688	0.657	16.1	0.677	0.643	16.6
11	0.282	0.752	0.723	15.1	0.743	0.710	15.6
12	0.300	0.808	0.781	14.1	0.800	0.770	14.6

From the last the last row of the operating characteristics of the stopping rule, it is seen that when the probability of toxicity  $>0.30$ , the trial will be halted with power of 0.81 based on the low boundary with expected sample size at the termination of 14.1 patients. Based on the high boundary, the trial in the expansion cohort will be terminated when the probability of toxicity more than 0.30 with a power of 0.77 at expected sample size of 14.6. If the trial toxicity is at least 0.30, the probability that the trial will cross the boundaries is at least 80%. These operating characteristics seem reasonable to stop the trial early for safety for a moderate sample of 24 patients.

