### **13. REPORTING OF ADVERSE EVENTS**

#### **13.1 ASSESSMENT OF SAFETY**

Safety assessments will consist of monitoring and reporting AEs and SAEs, including all events of death, pregnancy, and any study-specific issue of concern using Common Terminology Criteria for Adverse Events (CTCAE) version 4.0

All data will be collected in a timely manner and reviewed by the principal investigator and/or protocol chairperson every 2 weeks. In addition, there will be weekly meetings with the investigators, research nurse, protocol chairperson, and principal investigator to discuss patient issues, as well as important adverse events and trends in the data.

Safety assessments will consist of monitoring and recording all adverse events, including serious adverse events, the monitoring of hematology, blood chemistry, ECG and the regular monitoring of vital signs, and physical condition.

AEs, as reported throughout the course of the trial will be listed individually, per treatment group. Pre-, study and post-study findings of physical examination, vital sign variables, laboratory variables (hematology, clinical chemistry and urinalysis), and 12-lead ECG will be listed individually and summarized; values outside the normal range will be listed.

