#### **14.6.5 Data Safety Monitoring**

The Georgetown Lombardi Comprehensive Cancer Center will be responsible for the data and safety monitoring of this multi-site trial. As this study is an investigator initiated Phase I or II study utilizing a non-FDA approved drug for which the PI holds the IND it is considered a high risk study which requires real-time monitoring by the PI and study team and reviewed every 4 months by the LCCC Data and Safety Monitoring Committee (DSMC).

The Principal Investigator and the Co-Investigators will review the data including safety monitoring at their weekly institution based disease group meetings and on monthly disease group teleconferences.

All Severe Adverse Events (SAEs) are required to be reported to the IRB. Based on SAEs, the IRB retains the authority to suspend further accrual pending more detailed reporting and/or modifications to further reduce risk and maximize the safety of participating patients.

Progress on the trial and the toxicities experienced will be reviewed by the LCCC Data and Safety Monitoring Committee every 4 months from the time the first patient is enrolled on the study. Results of the DSMC meetings will be forwarded to the IRB with recommendations regarding need for study closure.

DSMC recommendations should be based not only on results for the trial being monitored as well as on data available to the DSMC from other studies. It is the responsibility of the PI to ensure that the DSMC is kept apprised of non-confidential results from related studies that become available. It is the responsibility of the DSMC to determine the extent to which this information is relevant to its decisions related to the specific trial being monitored.

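### Table 2's early-stopping and expected-sample-size columns assume a check after every patient, but the written rule has four looks; the quoted 0.81 and 14.1 belong to a boundary that is not shown.

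*Combined protocol and SAP*

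**What the plan says.** Section 12, Stopping Guidelines, plans for at most 24 expansion patients. It takes 10% toxicity as acceptable and 30% as unacceptable, with a "10% alpha level, i.e. probability of crossing the boundary under assuming acceptable toxicity is 10.0" per cent and 80% power.

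Table 1 lists four numbered monitoring looks, at 5, 11, 17 and 24 patients. The column headed "Stop if Number of Toxicities is at least" gives 3, 4, 5 and 6. The text below it repeats the rule at those four points only.

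Table 2 gives operating characteristics for a low and a high boundary: probability of crossing, probability of stopping, and expected sample size, at 12 toxicity rates from 0.10 to 0.30. At 0.30 the low boundary shows 0.808, 0.781 and 14.1, and the high boundary 0.800, 0.770 and 14.6. The plan does not say which of the two Table 1 is, and it lists no second boundary.

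For the low boundary the text says that "the trial will be halted with power of 0.81 based on the low boundary with expected sample size at the termination of 14.1 patients". For the high boundary it says the cohort ends "with a power of 0.77 at expected sample size of 14.6". It adds that at 30% toxicity or more "the probability that the trial will cross the boundaries is at least 80" per cent.

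Elsewhere, section 13.1 says "there will be weekly meetings with the investigators" and provides for data review every two weeks. Section 14.6.5 says the study "requires real-time monitoring by the PI and study team", with committee review every four months.

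**The concern.** One boundary is written down and two sets of operating characteristics are reported. The text takes its first pair of figures from one set and its second pair from the other. It calls 0.81 and 0.77 both power, although in Table 2 the first is a crossing probability and the second a stopping probability.

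This is the expansion cohort's numerical safety rule, and the plan defends it as reasonable for stopping early. The figures behind that defence are how often it stops early and how many patients it exposes. If they describe a different monitoring schedule, those approving the plan have been shown a more protective rule than the one written. Two teams could also run the rule differently, one acting only at 5, 11, 17 and 24 patients and the other after each patient.

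**Working it through.** **Inputs.** From Tables 1 and 2 and the surrounding text: N = 24; thresholds 3, 4, 5 and 6 at n = 5, 11, 17 and 24; 12 equally spaced toxicity rates from 0.10 to 0.30.

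**Method.** Exact binomial recursion. Carry forward the distribution of the toxicity count among cohorts not yet stopped. At each look, remove the probability at or above the threshold; call it c(n).
- Crossing = sum of c(n) over all looks.
- Early stopping = the same sum without the last look.
- E[N] = sum of n × c(n) over looks before the last + 24 × (1 − early stopping).

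**Reproducing the printed high-boundary figures.** Apply the Table 1 thresholds after every patient (3 up to patient 5, 4 up to 11, 5 up to 17, 6 up to 24). At 30% this gives crossing 0.7996, early stopping 0.7700 and E[N] 14.61, against printed 0.800, 0.770 and 14.6. At 10% it gives 0.0467, 0.0429 and 23.52, against printed 0.047, 0.043 and 23.5. All three columns match in all 12 rows, so Table 1 is the high boundary and Table 2 was computed for per-patient checking.

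**Four looks as written, 30% toxicity.**
- Look 1: P(X ≥ 3 of 5) = 0.1323 + 0.0284 + 0.0024 = 0.1631.
- Looks 2, 3 and 4, by recursion: 0.2829, 0.1977, 0.1559.
- Crossing = 0.1631 + 0.2829 + 0.1977 + 0.1559 = 0.7996.
- Early stopping = 0.1631 + 0.2829 + 0.1977 = 0.6437.
- E[N] = 5 × 0.1631 + 11 × 0.2829 + 17 × 0.1977 + 24 × 0.3563 = 0.82 + 3.11 + 3.36 + 8.55 = 15.84.

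| | Crossing | Early stopping | E[N] |
|---|---|---|---|
| 30%: printed, high boundary | 0.800 | 0.770 | 14.6 |
| 30%: four looks | 0.800 | 0.644 | 15.8 |
| 10%: printed, high boundary | 0.047 | 0.043 | 23.5 |
| 10%: four looks | 0.047 | 0.034 | 23.6 |
| Rows matched by four looks | 12 of 12 | 0 of 12 | 0 of 12 |

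Crossing is the same under both schedules because each threshold rises only after its look. A count reached between looks is still at or above the threshold at the next look. Only the timing changes.

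**Effect of the timing, 30% toxicity.** The gap of 0.770 − 0.644 = 0.126 is the share of cohorts that reach the stopping count before patient 24 but are declared only at patient 24. In 1,000,000 simulated cohorts, among those stopped at looks 1 to 3, 69% enrolled at least one patient after the count had been reached (mean 1.4, maximum 4).

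**The low boundary.** Its columns match Table 1 in no row under either schedule. A search of 1,330 boundaries with counts 3, 4, 5, 6 ending at patient 24, under both schedules, found one full match: 3 by patient 6, 4 by 11, 5 by 18 and 6 by 24, checked per patient. It gives 0.808, 0.781 and 14.1 at 30%, which is where the text's 0.81 and 14.1 come from.

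**The case against.** Table 2 contains no miscalculation: its high-boundary columns are exact for the Table 1 thresholds checked after each patient. That may be what was intended. A condition of at least 4 among the first 11 can be read as met when the fourth event occurs. Sections 13.1 and 14.6.5 describe frequent safety review, and the reference list includes a methods paper on continuous toxicity monitoring. On that reading 0.77 and 14.6 are correct, and the enrolment-after-crossing figures, which suppose that nobody acts between looks, fall away. Alpha and power are unaffected in any case, expected N moves by only 1.2 patients, the text does attribute 0.81 to the low boundary, and the same paragraph gives the 80% crossing statement.

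Much of this stands. The fault is a mismatch between table and rule, and it leaves overall error control intact. But Table 1 numbers four looks and gives the patient count at each, the text repeats only those four points, and no section says the boundary is applied between them. The review meetings concern general safety, and section 12 does not cite the methods paper. A reader following the plan as written would apply four looks. Naming the low boundary does not help when it is never shown.

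**Conclusion.** The concern holds. For the four looks as written, Table 2 overstates early stopping at 30% toxicity by 12.6 percentage points (0.770 against 0.644) and understates expected N by about 1.2 patients (14.6 against 15.8). At 10% toxicity the differences are small (0.043 against 0.034; 23.5 against 23.6). Power of 0.80 and attained alpha of 0.047, under the 10% ceiling, are correct for Table 1 under either schedule. The 0.81 and 14.1 belong to a boundary the plan does not contain. Like for like, Table 1's power is 0.80, and 0.77 is an early-stopping probability.

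These results assume independent patients with a common toxicity rate and each outcome known before the next enrolment. The plan gives no figure for pending outcomes. If, as an assumption, 1 or 2 further patients enrol while an outcome is pending, then at 30% toxicity per-patient checking gives E[N] of 15.4 or 16.1 and early stopping of 0.74 or 0.71. Four looks give E[N] of 16.5 or 17.1, with early stopping still 0.64.

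This should be fixed, but it does not invalidate the design.

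**What to change.** State in section 12 when the toxicity count is compared with the boundary, and make Table 2 and the text agree. The sponsor can choose either course:

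- **Per-patient checking.** Say that the Table 1 thresholds apply after each patient (3 in up to 5, 4 in up to 11, 5 in up to 17, 6 in up to 24). Keep the high-boundary columns, and note that 0.77 and 14.6 assume each outcome is known before the next enrolment. The cost is a running toxicity count updated for each patient.
- **Four looks.** Keep Table 1 and recompute the early-stopping and expected-N columns, giving 0.64 and 15.8 at 30% toxicity. The cost is publishing less favourable figures.

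Under either course:

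- Label Table 1 as the high boundary.
- Delete the low-boundary columns and the sentence with 0.81 and 14.1, or print that boundary and say what it is for.
- Report power as 0.80, and call 0.77 (or 0.64) the probability of stopping early.
- State the attained alpha of 0.047 beside the 10% ceiling.

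The boundary, alpha, power and sample size do not change.
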